## **Overview of Study**

[figure not shown]
In the proposed project we will evaluate the feasibility of IVR and assess the initial effects of IVR on symptoms, affect, and tolerance to cutaneous stimuli. In this single-arm trial, we will recruit 20 adults with CBP. Prior to their IVR experience, subjects will complete multiday baseline assessments using ecological momentary assessment (EMA) methodology to establish typical levels of symptoms and affect. They will return for two counterbalanced IVR sessions: one 10-minute and one 20-minute. Immediately after each session we will measure current symptoms and affect using valid and reliable self-report questionnaires, and we will measure changes in tolerance to cutaneous stimuli using quantitative sensory testing. We will measure symptoms and affect for 72 hours after each experimental session using EMA to determine if there is a carryover. At the completion of this study, we will continue to work with stakeholders to develop clinically relevant IVR interventions for people with CBP. Our study will have two aims:

Aim 1: Determine the feasibility and clinical usability of using IVR as an intervention for people with CBP.

Aim 2a: Examine the magnitude of the effects of IVR on symptoms, affect, and tolerance to cutaneous stimuli.

2b: Examine the effect of dosage (10 min, 20 min) on symptoms, affect, and tolerance to cutaneous stimuli.

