## Grant Flow Chart

**Study Design:** This is a cross-over feasibility trial.

**Subjects:** We will recruit 20 people with chronic back pain.

**Inclusion/Exclusion criteria:** Inclusion criteria: 30 to 65 years old; Low Back Pain that has lasted greater than 3 months due to non-cancer related injury or illness. Exclusion criteria: People with back pain due to rheumatic (e.g. rheumatoid arthritis or fibromyalgia) or central neurological disorders (e.g. stroke, multiple sclerosis, spinal cord injury); vision to see IVR programs; insufficient upper extremity coordination to operate IVR controls; insufficient cognitive ability to answer questionnaires or learn to use the IVR; unable to understand and respond to English. Subjects must have access to a cell phone or tablet for baseline and follow-up EMA testing. There are no exclusion criteria based on sex, race, ethnicity, or sexual orientation.

**Recruitment:** Throughout the grant we will work with Tufts CTSI Recruitment and Retention Support Unit (RSSU) to devise customized, multi-modality strategies to minimize accrual time and maximize participant retention in research studies. Strategies include: 1) We will access the Brigham & Women's Chronic Pain Registry and mail letters to appropriate candidates. 2) We will query the Tufts Medical Center's Clinical Academic Research Enterprise Trust (CLARET) data warehouse to identify eligible patient population. The CLARET is a centralized clinical data warehouse that aggregates clinical information from various Tufts Medical Center's systems. 3) The Tufts Medical Center website publicly posts general information about all research studies so that people can identify and contact studies. 4) We will deploy targeted advertising using Facebook Ads; 5) We will place fliers/advertisement placed in the following CBP program waiting areas: Brigham & Women's, Tufts Chronic pain, Medford Chronic pain.

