#### *Protocol*

Visit 1 (remote): We will obtain informed consent. Subjects will complete surveys on demographics and symptoms (pain, fatigue) and affect. Subjects will be randomly assigned to receive the 10 min or 20 min IVR session first.

We will also upload the EMA technology onto the subject's phone or tablet. Visit 1 will take up to ~1 hour.

Multiple Baseline EMA: Visit 2 will be scheduled 1-2 weeks later. During the time between visits we will use ecological momentary assessment (EMA) technology to collect multiple measures of pain, fatigue and affect. In EMA subjects respond to prompts delivered through their cell phone or tablet ("pings") with documentation of current symptoms. It is a well-recognized method to capture immediate, synchronized experiences in subjects' natural environments. During this data collection period subjects will be "pinged" 3x daily and asked to rate their current levels of pain, fatigue, and affect. Time to complete these responses will be less than 5 minutes.

Visit 2: We will collect current pain, pain interference, fatigue and affect, and QST. Subjects will receive an IVR session lasting either 10 or 20-min depending upon randomization. They will rate their current pain, fatigue, and affect, and we will complete QST. At the end of both sessions the subjects will rate their experiences of immersion using the Igroup Presence Questionnaire, engagement using the Use Engagement Scale (UES), and simulation tolerance using the Simulator Sickness Questionnaire (SSQ). Visit 2 will take about ~1 hour.

Post Visit 2 EMA: Subjects will complete three more days of 3x a day prompts for pain, fatigue and affect.

After Visit 2 we will follow-up with subjects using EMA for at least 72 hours to determine if there is any carryover of effect of IVR. This period will also act as a washout period before returning for the third visit.

Visit 3 will be the same as Visit 2. Participants will complete 10- or 20- minutes of VR depending upon randomization. We will complete a short semi-structured interview.

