#### *Analysis*

**Aim 1 - Feasibility:** We will identify the number of people from each referral source who contacted study personnel, volunteered to participate, and signed the consent. We will assess adherence to study protocols, including percentages completing outcome measures (including EMA) and completing both visits. We will assess IVR tolerance using the Simulator Sickness Questionnaire, pain threshold testing tolerance through direct questions, and the degree to which subjects felt engaged in the experience using the Igroup Presence Questionnaire. We

will determine how long it takes to complete the various parts of the study and how many breaks or incompletes occur during the intervention protocol. We will also examine expectations and perceptions of the IVR experience using open-ended questions.

*Aim 2 - Effect:* We will calculate effect sizes to compare baseline data to scores obtained immediately after completing IVR sessions. Symptoms and affect: We will examine the immediate effect of the IVR sessions by comparing the baseline symptom data with scores taken after completing the session. Tolerance to cutaneous sensory input: We will assess baseline and pre-session pain threshold levels with immediate post session measurements. To examine differences related to dosage, we will calculate an effect size between those who received the 10-minute IVR and those who received the 20-minute IVR session.

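### Aim 2a and the Aim 2 analysis call a baseline-to-post-session change the effect of IVR, although no condition is IVR-free; the claim should be narrowed to uncontrolled pre-to-post change

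*Combined protocol and SAP*

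**What the plan says.** The Overview of Study describes one group: "In this single-arm trial, we will recruit 20 adults with CBP". The Grant Flow Chart adds "This is a cross-over feasibility trial". What is crossed over is session length: "They will return for two counterbalanced IVR sessions: one 10-minute and one 20-minute". The Protocol section randomises only the order: "Subjects will be randomly assigned to receive the 10 min or 20 min IVR session first". No sham, waiting or other IVR-free condition is described.

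Aim 2a is to "Examine the magnitude of the effects of IVR on symptoms, affect, and tolerance to cutaneous stimuli". The Analysis section carries it out as follows: "We will calculate effect sizes to compare baseline data to scores obtained immediately after completing IVR sessions". For symptoms and affect it says: "We will examine the immediate effect of the IVR sessions by comparing the baseline symptom data with scores taken after completing the session". For QST it sets post-session thresholds against both a baseline and a pre-session value. It does not say which measurement is the baseline, and it places no limit on how the change may be interpreted.

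Three other features of the schedule matter here:

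- EMA runs three times a day for the 1-2 weeks before Visit 2 and covers pain, fatigue and affect. Its stated purpose is to establish usual levels.
- QST is listed under Outcome measures as a session measurement. Visit 1 is remote, and no QST is listed for it.
- The time between Visits 2 and 3 is used both to look for carryover and as a washout of at least 72 hours.

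**The concern.** A pre-to-post change estimates an IVR effect only if scores would otherwise have stayed the same. This protocol gives several reasons why they might not. QST and symptom ratings are repeated within a visit of about an hour. Subjects know they are receiving IVR and choose an experience that appeals to them. They spend 10 or 20 minutes away from ordinary activity, and chronic back pain varies from day to day. The Analysis section plans to ask about expectations but does not connect the answers to the effect estimate.

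What is at stake is the conclusion on a stated aim. Followed as written, the plan would report all of the change as the magnitude of the IVR effect. The undefined baseline adds to the problem: if it means EMA or the Visit 1 survey, the comparison also mixes a home or remote rating with one made at the session.

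**Working it through.** **1. What the design identifies.** Write the mean change at a session of length L as change(L) = e(L) + s(L). Here e is the effect of IVR and s is everything else that moves scores between the two measurements.

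- Aim 2a uses change(10) and change(20). Each has two unknowns, and no observed condition has e = 0. Neither e(10) nor e(20) can be recovered.
- Aim 2b uses change(20) − change(10) = [e(20) − e(10)] + [s(20) − s(10)]. Non-specific components common to both sessions cancel, and randomised order protects against period trends, provided carryover is negligible. This is a legitimate estimate of the effect of a 20- rather than a 10-minute session. It does not show whether either differs from no IVR.

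**2. Possible meanings of baseline.**

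| Candidate | Setting | Symptoms and affect | QST |
|---|---|---|---|
| Visit 1 survey, 1-2 weeks before Visit 2 | Remote | Yes | Not listed |
| EMA series before Visit 2 | Daily life | Pain VAS, PROMIS Daily Fatigue, PANAS | No |
| Pre-session score | Same visit | Yes | Yes |

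Only the pre-session score shares its setting and day with the post-session score, and only it exists for QST. Pain interference is listed before the session but not after it, so no session change is described for that scale.

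**3. IVR-free intervals.**

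- Before Visit 2: 3 × 7 = 21 to 3 × 14 = 42 prompts per subject, all IVR-free, for the three EMA outcomes only.
- Visit 2 pre-session to Visit 3 pre-session: contains the first IVR session and any carryover, so it is not IVR-free.
- QST therefore has no IVR-free interval anywhere in the schedule.

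**4. How a non-specific shift would appear.** The plan gives 20 subjects without alpha, power, SD or precision target, so there is no stated figure to reproduce. The following is an illustration.

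- Inputs: n = 20 (documents); two-sided 5% and normally distributed changes (assumed); shift δ in units of the SD of change, with e = 0 (assumed range).
- Half-width of the 95% interval for the mean change: t(0.975, 19)/√20 = 2.093/4.472 = 0.468 SD of change.
- Probability that the interval excludes zero, where F is the noncentral t distribution function: 1 − F(2.093; 19 df, δ√20) + F(−2.093; 19 df, δ√20).

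| Assumed δ | δ√20 | Probability interval excludes 0 when IVR does nothing |
|---|---|---|
| 0 | 0 | 0.050 |
| 0.2 | 0.894 | 0.136 |
| 0.3 | 1.342 | 0.247 |
| 0.5 | 2.236 | 0.565 |
| 0.8 | 3.578 | 0.924 |

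Bias in the point estimate is simply δ, whatever the sample size. Recruiting more subjects would not remove it.

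**The case against.** The best defence is that the plan is open about its design and modest in its ambition. It calls itself single-arm and a feasibility trial, it speaks of initial effects, and it plans effect sizes with no hypothesis test, success threshold or efficacy claim. Effect size is also the ordinary term for a standardised pre-to-post difference. This stands as a reason to keep the point moderate and not to ask for a control arm. It does not answer the wording of Aim 2a or of the symptom analysis, both of which attribute the change to IVR without qualification.

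A reader might also infer stronger things that the documents do not support:

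- *That only pre-to-post change is measured.* EMA before and after sessions and a randomised-order dose contrast are also collected. It is the Aim 2a analysis that rests on baseline-to-post change.
- *That the Visit 2 to Visit 3 pre-session change can serve as a no-IVR reference for QST.* That interval includes an IVR session and the period in which the protocol itself looks for carryover.
- *That change from Visit 1 to Visit 2, or the EMA series, can act as a control.* Remote surveys and prompts hours apart in daily life do not reproduce same-visit repeat testing, time in the session or expectation about the headset. They show natural fluctuation and drift at most.
- *That an inflated effect size will mis-size a later controlled trial.* The only next step stated is further work with stakeholders on developing IVR interventions. Any per-arm figure would need an assumed observed change, an assumed non-specific part and an assumed standardising SD.

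**Conclusion.** The point holds as a matter of interpretation. With IVR given at every session and only its duration order randomised, the baseline-to-post-session change cannot be separated from repeat testing, expectation, setting and natural fluctuation, so it should not be reported as the effect of IVR. The conclusion follows from the schedule and needs no numerical assumption.

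The size of the distortion is unknown. The probabilities of 0.14 to 0.92 rest on assumed shifts of 0.2 to 0.8 SD of change and on an interval that the plan does not itself call for. They show only that an apparently clear change could arise without any IVR effect. No stated number in the plan is wrong, and Aim 1 is untouched. The change is worth making because it alters what Aim 2a can conclude and costs very little.

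**What to change.** 1. Reword Aim 2a, the Aim 2 part of the Analysis section and the resulting conclusion to uncontrolled pre-to-post change around an IVR session.
2. Define baseline for this purpose as the same-visit pre-session score, for every outcome measured both before and after the session.
3. Reserve the word effect for the within-subject 20 versus 10 minute contrast.
4. For pain VAS, PROMIS Daily Fatigue and PANAS only, report within-person change and variability in the 1-2 week EMA series before Visit 2 beside the session change. Label it a descriptive benchmark of natural fluctuation and drift, not a control, and do not subtract it to obtain an IVR effect.
5. State that QST has no IVR-free reference interval in this schedule, because Visit 1 is remote with no QST listed and Visit 2 to Visit 3 contains an IVR session. Its change is therefore uncontrolled.

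No new visits, measurements or subjects are needed. The cost is a more modest claim and one small descriptive analysis.

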## Grant Flow Chart

**Study Design:** This is a cross-over feasibility trial.

**Subjects:** We will recruit 20 people with chronic back pain.

**Inclusion/Exclusion criteria:** Inclusion criteria: 30 to 65 years old; Low Back Pain that has lasted greater than 3 months due to non-cancer related injury or illness. Exclusion criteria: People with back pain due to rheumatic (e.g. rheumatoid arthritis or fibromyalgia) or central neurological disorders (e.g. stroke, multiple sclerosis, spinal cord injury); vision to see IVR programs; insufficient upper extremity coordination to operate IVR controls; insufficient cognitive ability to answer questionnaires or learn to use the IVR; unable to understand and respond to English. Subjects must have access to a cell phone or tablet for baseline and follow-up EMA testing. There are no exclusion criteria based on sex, race, ethnicity, or sexual orientation.

**Recruitment:** Throughout the grant we will work with Tufts CTSI Recruitment and Retention Support Unit (RSSU) to devise customized, multi-modality strategies to minimize accrual time and maximize participant retention in research studies. Strategies include: 1) We will access the Brigham & Women's Chronic Pain Registry and mail letters to appropriate candidates. 2) We will query the Tufts Medical Center's Clinical Academic Research Enterprise Trust (CLARET) data warehouse to identify eligible patient population. The CLARET is a centralized clinical data warehouse that aggregates clinical information from various Tufts Medical Center's systems. 3) The Tufts Medical Center website publicly posts general information about all research studies so that people can identify and contact studies. 4) We will deploy targeted advertising using Facebook Ads; 5) We will place fliers/advertisement placed in the following CBP program waiting areas: Brigham & Women's, Tufts Chronic pain, Medford Chronic pain.

#### **Outcome measures**

Our study will include feasibility measures and magnitude of effect measures: Feasibility measures will examine the practicalities of investigating implementation of IVR for people with CBP and subjects' preferences and tolerance to the protocol.

Item	Measurements
Recruitment	Responses to different recruitment methods; # contacting study; # coming to study; # consented; Recruitment generating appropriate subjects; # willing to be randomized
Adherence/Fidelity	Immersion into VR (Igroup Presence Questionnaire [IPQ]); Engagement in IVR (User Engagement Scale [UES]); # of breaks; # of subjects completing study; Completeness of data collection
Burden	Length of time to complete measures, length of time for ecological momentary assessment (EMA) responses, subjects' perception of burden (open-ended questions)
Tolerance	Tolerance to IVR (Simulator Sickness Questionnaire [SSQ]); minutes in IVR experience; tolerance to Quantitative Sensory Testing (QST); open-ended question responses
Stakeholder input	Open ended questions about perceptions and preferences.

Measures for the magnitude of effect will address symptoms, affect and tolerance to cutaneous stimuli. All the proposed measures are valid and reliable measures of the proposed construct.

Item	Measurements
Symptoms	
Pain	Pain Visual Analogue Scales (VAS) (EMA and Session), PROMIS pain interference scale (Session)
Fatigue	PROMIS Daily Fatigue Scale (EMA and Session), PROMIS Fatigue Scale

Affect	(Session) Positive and Negative Affect Scale (PANAS) (EMA and Session)
Quantitative Sensory Testing (QST) (Session)	
Hyperalgesia	Mechanical Pressure Pain Thresholds (MPPTh) will be assessed using a digital pressure algometer on the right upper trapezius and right thumb MP joint. Mechanical Temporal Summation of Pain (MTSP) will be assessed using weighted pinprick stimulators. We will apply a train of 10 stimuli at the rate of 1 per second on the middle finger of the right hand, and subjects will rate the painfulness of the first, fifth, and tenth stimulus.

### *Intervention Immersive Virtual Reality (IVR)*

Our IVR experiences will be delivered with the Oculus RiftS system (headset and hand controllers) using commercially available VR software. IVR sessions will last either 10 or 20 minutes. Subjects will select an IVR experience that appeals to them.

#### *Protocol*

Visit 1 (remote): We will obtain informed consent. Subjects will complete surveys on demographics and symptoms (pain, fatigue) and affect. Subjects will be randomly assigned to receive the 10 min or 20 min IVR session first.

We will also upload the EMA technology onto the subject's phone or tablet. Visit 1 will take up to ~1 hour.

Multiple Baseline EMA: Visit 2 will be scheduled 1-2 weeks later. During the time between visits we will use ecological momentary assessment (EMA) technology to collect multiple measures of pain, fatigue and affect. In EMA subjects respond to prompts delivered through their cell phone or tablet ("pings") with documentation of current symptoms. It is a well-recognized method to capture immediate, synchronized experiences in subjects' natural environments. During this data collection period subjects will be "pinged" 3x daily and asked to rate their current levels of pain, fatigue, and affect. Time to complete these responses will be less than 5 minutes.

Visit 2: We will collect current pain, pain interference, fatigue and affect, and QST. Subjects will receive an IVR session lasting either 10 or 20-min depending upon randomization. They will rate their current pain, fatigue, and affect, and we will complete QST. At the end of both sessions the subjects will rate their experiences of immersion using the Igroup Presence Questionnaire, engagement using the Use Engagement Scale (UES), and simulation tolerance using the Simulator Sickness Questionnaire (SSQ). Visit 2 will take about ~1 hour.

Post Visit 2 EMA: Subjects will complete three more days of 3x a day prompts for pain, fatigue and affect.

After Visit 2 we will follow-up with subjects using EMA for at least 72 hours to determine if there is any carryover of effect of IVR. This period will also act as a washout period before returning for the third visit.

Visit 3 will be the same as Visit 2. Participants will complete 10- or 20- minutes of VR depending upon randomization. We will complete a short semi-structured interview.

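### No stated step keeps session length from the subject or the QST examiner, so expectation can enter the 10 versus 20 minute contrast, whose outcomes all rest on subject response

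*Combined protocol and SAP*

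**What the plan says.** The combined protocol and SAP calls the study single-arm in the Overview ("In this single-arm trial, we will recruit 20 adults with CBP") and a cross-over in the Grant Flow Chart ("This is a cross-over feasibility trial"). Each subject is to have both session lengths, and what is randomised is their order. The Protocol section places the assignment at Visit 1: "Subjects will be randomly assigned to receive the 10 min or 20 min IVR session first". The first session comes later: "Visit 2 will be scheduled 1-2 weeks later". Visit 3 repeats Visit 2 with the other length: "Participants will complete 10- or 20- minutes of VR depending upon randomization".

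At each session visit the team takes ratings and QST, gives the IVR session, and measures again: "They will rate their current pain, fatigue, and affect, and we will complete QST". No separate or masked examiner is named. Nothing is said about whether the subject is told the order or the length.

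On outcomes, the Overview states: "Immediately after each session we will measure current symptoms and affect using valid and reliable self-report questionnaires". Under Outcome measures, temporal summation is a rating: "subjects will rate the painfulness of the first, fifth, and tenth stimulus". Pressure pain threshold is read from a digital algometer, and the text does not say how the subject signals that the threshold is reached.

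The Analysis section plans an effect size for 10 against 20 minutes, with no test, interval or decision rule. Under Aim 1 it also plans open-ended questions about what subjects expect and how they find IVR.

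**The concern.** The two lengths are the only conditions compared by randomisation; Aim 2a is an uncontrolled comparison with baseline. If a subject knows which length is being given and expects more, or less, from the longer one, that expectation belongs to the length itself. It therefore travels with the 20-minute session at whichever visit that session falls. An examiner who knows the length could add to it through the way the pressure test is applied or cued.

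At stake is the meaning of the Aim 2b effect size. It could reflect minutes of IVR, expectation about minutes, or both, and the plan has no quantitative measure to help tell them apart. Both conditions are IVR and differ only in duration, and the headset hides the room, so partial masking is possible where it would not be for IVR against no IVR.

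**Working it through.** **1. What the text says about masking.** The Overview, Grant Flow Chart, Outcome measures, Intervention, Protocol and Analysis sections mention no blinding, no concealment of the order and no independent examiner. The consent pages and one opening part of the document are not in the text available for review, so the absence is established only for these sections.

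**2. How each Aim 2 outcome arises.** Pain VAS, the PROMIS scales and PANAS are self-report. Temporal summation is a subject rating. Pressure pain threshold is measured by a device, but a pain threshold needs the subject to indicate pain. None is independent of the subject.

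**3. Does the design remove expectation?** I read the dose contrast as within-subject, since everyone is planned to have both lengths. Let δ be the true 20-minus-10 effect, e the net expectation difference between lengths, and p1, p2 the period effects. Ignoring carryover, the expected 20-minus-10 difference is:

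- order 10 then 20: δ + e + (p2 − p1)
- order 20 then 10: δ + e − (p2 − p1)
- mean of the two orders: δ + e

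The cross-over removes stable differences between people, and balanced order removes the period effect. The term e stays in full at any sample size.

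**4. Which measurements are exposed?** The baseline EMA, B, is collected once, before Visit 2. If it is the reference for both sessions, (Y20 − B) − (Y10 − B) = Y20 − Y10, and B drops out. If change is taken from pre-session values, the contrast carries e(post) − e(pre). A shift that occurs only before the session can then act against the 20-minute condition. The exposed values are the pre-session and post-session measures at each visit.

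**5. Illustration on assumed values.** The plan gives no SD, correlation, alpha, power or VAS range, so there is no figure of its own to reproduce.

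(a) Assume a 0-100 VAS, an SD of the paired difference of 20, and e from 2 to 8 points. Then 2/20 = 0.10 and 8/20 = 0.40 SD. With 20 subjects the standard error is 20/√20 = 4.47 points, and the 95% half-width is 2.093 × 4.47 = 9.36 points. A shift of this size would lie within the sampling error of one trial.

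(b) Assume SD 1 for a single measurement, within-subject correlation ρ, no dropout, δ = 0 and a two-sided 5% level. SE = √(2(1 − ρ)/20), and the half-width is 2.093 × SE. The last three columns give the chance that a nominal 95% interval excludes zero (noncentral t).

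| ρ | SE | Half-width | e = 0.2 SD | e = 0.3 SD | e = 0.5 SD |
|---|---|---|---|---|---|
| 0.3 | 0.265 | 0.55 | 11% | 19% | 43% |
| 0.5 | 0.224 | 0.47 | 14% | 25% | 57% |
| 0.7 | 0.173 | 0.36 | 20% | 38% | 78% |

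The SD units in (a) and (b) coincide at ρ = 0.5, where √(2 × 0.5) = 1. No test is planned, so these percentages only show how a reader could be misled by an interval around the estimate.

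**The case against.** The strongest reply is that this is a 20-person feasibility study reporting an effect size with no test or decision attached, for which open-label delivery is defensible. A session twice as long is perceptible, and by Visit 3 the subject has a comparison. The pinprick procedure is standardised (ten stimuli, one per second, weighted stimulators), so examiner influence is plausible mainly for the pressure threshold. Withholding the lengths could also make the Aim 1 count of people who accept randomisation less informative.

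Most of this stands as a limit on severity. It does not remove the point, because Aim 2b is a stated aim, the changes are cheap, and a feasibility study is a sensible place to learn whether length can be masked. Subjects would still be consenting to two lengths in random order.

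A reader might infer several stronger claims that the documents do not support:

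- **That subjects are told the order at Visit 1.** The text records an assignment, not a disclosure, and the consent pages are not available.
- **That there will be no data on expectation.** The Analysis section plans open-ended questions. They are qualitative, have no stated timing and are not tied to the dose contrast, so they do not settle the matter, but they exist.
- **That foreknowledge during the baseline EMA biases the within-subject contrast.** A baseline shared by both sessions cancels (step 4).
- **That the bias favours 20 minutes.** Fatigue or simulator sickness after the longer session could act the other way.

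**Conclusion.** The point holds as a design improvement worth making, not as a flaw that undermines the study. As far as the available sections show, session order is set one to two weeks before the first session, no step keeps order or length from the subject or the QST examiner, and every Aim 2 outcome depends on subject response. Expectation tied to length can therefore enter the only randomised contrast, and neither randomised order nor the cross-over takes it out.

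Its size and direction cannot be derived from the documents. The 0.10 to 0.40 SD range follows entirely from the assumed shift and SD; it is an illustration, not an estimate. The consequence is a dose effect size that may combine length with expectation, rather than a failed confirmatory claim. The conclusion assumes a within-subject dose contrast and that the unseen pages contain no masking provisions.

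**What to change.** 1. Keep the order concealed from the subject and site staff until the pre-session ratings and QST at Visit 2 are complete, for example by sealed envelope or electronic release. This protects the Visit 2 pre-session values only; it does not mask the post-session QST, and the Visit 3 length then follows by elimination.
2. Describe the sessions to subjects as two sessions of different length, each up to 20 minutes. Do not announce which one is being given, and hide in-headset timers where possible.
3. Use a fixed script for post-session QST at both visits. Where staffing already allows, have it run by a team member who did not run the session.
4. At each visit record a short pre-session expectancy rating and, after the post-session measures, the perceived duration. Report both descriptively beside the dose contrast. Do not split the contrast by correct guess: that conditions on a post-treatment variable in at most 20 subjects, each with two guesses.
5. Disclose the lengths before the Visit 3 interview so that preferences about length can still be collected. Report Aim 2b as at best partly masked, with an effect size that may combine length and expectation.

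The cost is consent and script wording, an envelope or electronic release, and two brief items per visit. Session lengths, schedule and sample size do not change, and no new staff are required, although item 3 is stronger where a second person is already present. The downside is that masking will be partial, especially at the second session, and subjects learn the exact lengths only at the end.

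### The Simulator Sickness Questionnaire is given only after each IVR session, so a raised absolute score cannot be split into arrival symptoms and net change over the session

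*Combined protocol and SAP*

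**What the plan says.** The Outcome measures section lists the SSQ first under Tolerance, beside time spent in IVR, tolerance to QST and open-ended responses. The Analysis section (Aim 1 - Feasibility) names the SSQ as the instrument for IVR tolerance, and gives no SSQ cut-off or change score.

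The Protocol section sets the timing. The relevant sentence begins "At the end of both sessions the subjects will rate their experiences of immersion", goes on to engagement, and ends with "simulation tolerance using the Simulator Sickness Questionnaire (SSQ". The other assessment points are:

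- Visit 1: "Subjects will complete surveys on demographics and symptoms (pain, fatigue) and affect".
- Baseline EMA: participants are "asked to rate their current levels of pain, fatigue, and affect".
- Before the session at Visit 2: "Visit 2: We will collect current pain, pain interference, fatigue and affect, and QST".
- After the session at Visit 2: "They will rate their current pain, fatigue, and affect, and we will complete QST".
- Visit 3 repeats Visit 2 and adds a short interview.

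The Overview of Study describes the design: "In this single-arm trial, we will recruit 20 adults with CBP", and "They will return for two counterbalanced IVR sessions: one 10-minute and one 20-minute". Every participant receives IVR at both sessions.

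**The concern.** Tolerance is an Aim 1 outcome. A sickness score taken only after exposure combines what the participant brought to the visit with what changed during it. Pain, fatigue, affect and QST are each measured before and after the session, so for those the two parts can be separated. The SSQ also records symptoms but has no such pair, and no non-IVR session could serve as a reference.

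If post-session scores are low, nothing is lost. If they are raised, the team cannot tell whether the symptoms came with the participant or developed over the session, and might judge IVR less tolerable than it is. The missing value cannot be recovered after data collection.

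**Working it through.** The plan gives no figure for this point, so there is none to reproduce. The check is a listing of when the SSQ is given, followed by simple algebra.

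**Step 1: where the SSQ appears (Protocol section).**

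| Assessment point | Content | SSQ? |
|---|---|---|
| Visit 1 | demographics, pain, fatigue, affect | no |
| Baseline EMA | pain, fatigue, affect | no |
| Visit 2, before session | pain, pain interference, fatigue, affect, QST | no |
| Visit 2, after session | pain, fatigue, affect, QST, presence, engagement, SSQ | yes |
| EMA after Visit 2 | pain, fatigue, affect | no |
| Visit 3, before session | as Visit 2 | no |
| Visit 3, after session | as Visit 2, plus interview | yes |

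SSQ scores before IVR exposure on the day: 0. The timing phrase could be read as a single SSQ after the second session. It stands in the Visit 2 description, which Visit 3 repeats, so once after each session is the natural reading. The count of pre-session scores is 0 either way.

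**Step 2: what one score can identify.** Let A be the arrival score and C the net change from arrival to questionnaire. Then Post = A + C. One observation per session does not identify two terms. The post score exceeds the change by Post − C = A. If the scale starts at 0 (assumed; the documents do not give it), A ≥ 0, so the mean post score is an upper bound on the mean net change.

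**Step 3: symptoms that arose are a different quantity.** Write C = R − E, where R is what arose during the session and E is what eased before the questionnaire. Then R = Post − A + E. Whenever E is larger than A, R exceeds Post. This is possible here: the SSQ is listed after the post-session ratings and the repeat QST, which would leave time for symptoms to ease if that is the order followed.

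**Step 4: the 10- versus 20-minute contrast.** Within a person, Post20 − Post10 = (A20 − A10) + (C20 − C10). If arrival symptoms are stable, A20 − A10 = 0 and the contrast is unaffected. It does not recover the absolute level: an equal rise at both lengths gives C20 − C10 = 0.

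**Step 5: would a change score cost precision?** With 20 participants, the 95% half-width for a mean post score is t(0.975, 19)/√20 = 0.468 SD. For a mean change with equal pre and post SDs it is 0.468 × √(2(1 − r)), where r is the pre-post correlation. Equal SDs and all values of r are assumptions.

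| r (assumed) | Half-width of mean change (SD) |
|---|---|
| 0.3 | 0.554 |
| 0.5 | 0.468 |
| 0.7 | 0.363 |
| 0.8 | 0.296 |

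Under equal SDs the change is at least as precise as the post score when r is 0.5 or more. At r = 0.3 it is √1.4 = 1.18 times as wide. These figures describe the remedy; they say nothing about how large A is.

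**The case against.** The strongest reply is that no stated use of the SSQ is broken. It is one feasibility measure, with no promised change score, cut-off, progression rule or attribution to IVR. How people feel when they finish a session is a fair meaning of tolerance in a 20-person feasibility study. That stands: a reader might infer that the plan contradicts itself or that the tolerance outcome is uninterpretable, and the documents support neither.

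The error in the absolute score also runs in one direction. A reader might infer that IVR could be made to look better tolerated than it is; persisting arrival symptoms do the opposite. Nor is the comparison of session lengths invalid, since stable arrival symptoms cancel in it (step 4).

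A raised score would not be read alone either. Minutes in IVR, breaks, pre/post pain, fatigue and affect, open-ended questions and the interview all bear on tolerance. They help in part, but none supplies a pre-session SSQ value.

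Finally, asking about sickness symptoms just before exposure may prompt participants to notice or report them afterwards. This is a real drawback of adding the questionnaire, and the design cannot measure it.

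**Conclusion.** The point holds as an improvement to how an Aim 1 outcome can be read, not as a flaw that invalidates the plan. With no SSQ before exposure and no non-IVR condition, a raised absolute post-session score cannot be divided into arrival symptoms and net change. It overstates the net change by the unmeasured arrival component.

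The size of that component is unknown; any figure would rest wholly on assumed inputs. The practical consequence depends on two things that the documents do not establish: that post-session scores are raised, and that arrival symptoms contribute materially to them.

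One further inference should be resisted. A reader might take the post-session score as a ceiling on the symptoms that arose during the session. Step 3 shows that it is not, because symptoms that arose and then eased are missed. The bound applies only to mean net change, and only if the scale starts at 0.

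**What to change.** Add the SSQ to the measures taken before the session at Visits 2 and 3, and keep the post-session SSQ. Report the pre-to-post change for each session length alongside the post score. State that the change removes arrival symptoms but not effects of time, QST or repeated questioning, so without a non-IVR condition it is not proof of cause.

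The cost is one questionnaire already in use, repeated once at each of two visits of about 1 hour: a few more minutes, slightly more participant burden (itself a study outcome), and the possible prompting effect, which should be acknowledged in the report.

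If the pre-session SSQ is not added, describe the post-session score as symptoms present when the questionnaire is completed. If the scale is confirmed to start at 0, it may also be called an upper bound on mean net change from arrival to questionnaire. It should not be called an upper limit on symptoms that arose during the session. This alternative adds no burden.
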